9.2 Reporting

9.2.1 Adverse Events (AE) and Severe Adverse Events (SAE) Reporting

All serious AE, whether or not deemed expected or device-related, must be reported to the clinical monitor immediately or within 24 hours by telephone (see below). A written report must follow within five working days and is to include a full description of the event and sequence. If the Venus Concept monitor cannot be reached, the site personnel will directly contact the Regulatory manager of Venus Concept @ [name].

In addition to reporting adverse events within the context of this clinical study, 21 CFR Part 803 Medical Device reporting requirements and any applicable local device reporting requirements will be followed.

9.2.2 Device Malfunctions/Medical Device Reporting

Each device failure/adverse event will be assessed for possible reporting as a Medical Device Report (MDR), and a determination will be made in accordance with the Sponsor's standard operating procedure. MDRs will be reported in accordance with 21 CFR 803.

9.3 Risk/ Benefit Analysis

9.3.1 Risks

Eye injuries are possible to the operator, but should be entirely preventable by proper use of dedicated eye shields, which will be worn by staff/ subjects in the presence of laser irradiation.

The potential risks for adverse effects of the treatment procedure include but are not limited to blistering, burns, excessive edema or erythema, infection, scarring and PIH, as detailed above in the Anticipated Adverse Events section. In the case of an infection evolving in the treated area the subject will be provided antibiotics for the treatment of the infection at no cost.

9.3.2 Anticipated Benefits

If the subject agrees to participate in this study, he/she will be contributing to the understanding of the device's impact and the biological processes that are occurring in the different skin layers. This understanding may lead to optimization of the treatment of these devices. There is no direct benefit to the participating subjects.

10 Administrative Procedures

10.1 Investigator Selection

The investigator must be of good standing as an investigator and knowledgeable in relevant areas of clinical research to ensure adherence to the requirements of the protocol, including the protection of human subjects. Other site personnel must have appropriate research experience and infrastructure to ensure adherence to the protocol and enrollment of sufficient numbers of evaluable subjects. The curriculum vitae (CV) of the Investigator will be maintained in the Sponsor files as documentation of previous medical training, and federal databases will be searched to ensure that the investigator is in good standing with the FDA or as applicable. The Principal Investigator will sign the signature page of this protocol, agreeing to comply with all applicable government regulations and the requirements of this study.

10.2 Ethic committee Approval

This clinical study will be conducted according to all applicable regulations under 21CFR, the Medical Device Directive and in accordance with the ICH Good Clinical Practice and local laws and regulations relevant to the use of medical devices.

An Ethical Committee (EC or IRB) will approve the clinical study protocol prior to study initiation. Approval will be indicated in writing with reference to the final protocol number and date.

Details regarding the EC/IRB's constitution including the names of its members, their qualifications and what function they perform on the board (e.g., chairman, specialist, lay-member) will be made available to enable Venus Concept and the Investigator to conform to regulations governing research on experimental devices.

10.3 Informed Consent

Prior to the procedure, the Investigator must explain to each subject nature of the study, its purpose, expected duration, and the benefits and risks of study participation. After this explanation and before entering the study, the subject must voluntarily sign and date the approved Informed Consent form.

10.4 Subject Withdrawal/Dropouts

The subjects will be advised in the written Informed Consent form that they have the right to withdraw from the study at any time without prejudice, and may be withdrawn at the Investigator's/Venus Concept' discretion at any time. In the

event that a subject drops out of the study or is withdrawn from the study, the Exit/Termination CRF form should be completed. On the withdrawal page the Investigator should record the date of the withdrawal, the person who initiated withdrawal and the reason for withdrawal.

Reasonable effort should be made to contact any subject lost to follow-up during the course of the study in order to complete assessments and retrieve any outstanding data and study medication/supplies. The records of subjects who terminate prior to completing the study will be retained and the reason for termination will be documented.

The following are possible reasons for subject dropout/withdrawal:

- Adverse event that would prevent subject compliance with the protocol;
- Subject withdrawal of consent;
- Subject lost to follow-up (e.g., subject cannot be located or contacted and does not return for follow-up visits);
- Subject death;
- Investigator/Venus Concept requested subject to be withdrawn.

However, every effort should be made to see that subject is followed for the remainder of the study even if subject is unable or unwilling to comply with the protocol.

10.5 Case Report Forms/Data Collection

The Investigator is responsible for completely and accurately recording study data in the appropriate sections of the CRFs provided by Venus Concept. The CRFs must be signed by the Investigator or by his/her authorized person as designated in the Signature Authorization Log.

Data recorded on the CRF and photographs will serve as a source document for the study data.

The monitor will ensure the quality of data recording at each investigational site by comparison to supporting source documents during periodic site visits. Adherence to proper recording of information as well as assuring that corrections are being made will also be addressed during these periodic visits.

10.6 Required Documentation

Prior to starting the clinical study, the following documents must be submitted or returned to Venus Concept by the Investigator:

- Signed Clinical Trial Acknowledgement for the protocol
- Signed Clinical Evaluation Agreement
- Curriculum Vitae of the investigator
- Signed Financial Disclosure Statement
- IRB or other ethic committee Assurance of Compliance form or equivalent
- Written approval from the Ethical Committee of both the protocol and informed consent form

10.7 Subject's Financial Compensation

Subjects will not pay for any office visits, examinations and procedures as part of this clinical study.

Subjects may receive a stipend for participation in the study according to each site's standard procedures and IRB approval. Any such stipend will be detailed in the Informed Consent Form and Clinical Trial Agreement. Any subject stipend will be given after the last follow-up visit or after the subject's last visit as part of the study, whichever comes sooner.

10.8 Device Use/Accountability

The evaluation site personnel will maintain records of the model and serial number of the devices (if appropriate) used for treatment during the conduct of the study. The devices along with the associated delivery applicators and accessories are to be maintained by the research sponsor with reasonable care being taken by the Investigators and facility to prevent damage to, or unauthorized use of, the equipment. The equipment will be returned to the sponsor at the end of the study.

10.9 Training Requirements

Both the Investigator and the Sponsor, prior to any independent use of the device, will agree upon the Investigators' training requirements. Prior to the study, the sponsor will ensure the investigator has received in depth training on the use of the device.

10.10 Modification of Protocol

The protocol may be amended with the agreement of the sponsor and upon notification of and approval by the IRB or other relevant ethic committee.

Investigators should review the contents of this protocol. Subsequent alterations should only be made in written conjunction with the sponsor.

Medically significant amendments to the protocol (e.g., changes that increase the risk or the inconveniences for the patient, inclusion of new categories of patients, etc.) must be approved by the local IRB prior to implementation.

10.11 Data Retention/Archiving Data

The Investigator must keep the following documents in a secure place for at least two years after the last clearance of a marketing application or at least two years have elapsed since the formal discontinuation of clinical development of the investigational product.

A signed copy of the final protocol and amendments.

Copies of the subjects' evaluation forms, data clarification forms and any associated subject-related raw data or where applicable, authorized copies of raw data.

Clinical photographs stored on CD-ROM or similar electronic media.

The subjects' signed Informed Consent forms.

10.12 Site Monitoring

The study monitors are designated as agents of Venus Concept and are assigned to oversee the conduct and progress of the study and to be the principal communication link between Venus Concept and investigator. The study monitors will be involved in monitoring of sites and records, to ensure continued compliance with the protocol and adequacy of the investigator and the facility to carry out the study.

The study will be monitored by representatives of Venus Concept Medical, Ltd. by telephone, in writing and during on-site visits. At a minimum, site visits will be scheduled prior to the initiation of the study, on the occasion of the initial use of investigational devices, and at the end of the study. The purpose of site visits will be to ensure compliance with the investigational plan, to ensure appropriate use of investigational devices, and to inspect and retrieve study data.

10.13 Termination of Study

Venus Concept reserves the right to discontinue the study at any time for administrative or other reasons. Written notice of study termination will be submitted to the investigator in advance of such termination. Termination of a

specific site can occur because of (but is not limited to) inadequate data collection, low subject enrollment rate, achievement of the total enrollment, or non-compliance with the protocol or other clinical research requirements

10.14 Reporting Requirements

The investigator must promptly report to Venus Concept any withdrawal of IRB or other relevant ethic committee approval at the site. Additional reporting requirements include:

Notify Venus Concept's designee and to the IRB or other relevant ethic committee a report of any severe adverse device effect, whether anticipated or unanticipated, that occurs during the study as soon as possible, but in no event later than ten working days after the investigator first learns of the effect. This report is to include a description of the effect, subsequent treatments, clinical outcomes, and outcome diagnoses. If the site personnel are not sure whether an event meets these criteria they should call the clinical monitor.

Notify Venus Concept or Venus Concept's designee and the IRB or other relevant ethic committee immediately (within 24 hours) if an emergency situation arises in which the subsequent treatment, in the best interests of the subject, requires a deviation from the protocol. This should be followed with written confirmation that describes the emergency action and outcomes, to Venus Concept and the IRB or other relevant ethic committee within five working days.

Report to the IRB or other relevant ethic committee and Venus Concept, within five working days, the use of the study device without signed informed consent from the subject.

Report adverse events in accordance with 21 CFR 803.

Submit regular progress reports to the IRB and Venus Concept or Venus Concept's designee, as requested by the investigators or IRB or other relevant ethic committee.

Submitting a final report on the study to the IRB and Venus Concept or Venus Concept's designee within three months after termination or completion of the study.

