9.1.1 Severity

Each AE should be assessed for its severity, or the intensity of an event experienced by the subject.

Mild: Awareness of a sign or symptom that does not interfere with the subject's activity or is transient resolved without treatment and has no sequelae.

Moderate: May interfere with the subject's usual activity and require additional intervention and/or treatment, and may have additional sequelae.

Severe: Significant discomfort to the subject and/or interferes with the subject's activity. Additional intervention and or treatment are necessary. Additional sequelae occur. Severe is used to describe the intensity of an event experienced by the subject.

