9.1.3 Serious Adverse Events

NOTE: The term serious is not synonymous with severity, which may be used to describe the intensity of an event experienced by the subject). An AE that does not meet any of the below criteria will be classified as non-serious.

A serious AE is any event that:

- Results in, or contributes to a death;
- Is immediately life- threatening (injury or illness);
- Results in hospitalization, or prolongs an existing hospitalization;
- Results in permanent impairment of body structure or function, or in persistent or significant disability/incapacity;
- Results in an injury that requires medical intervention to prevent permanent impairment of body structure or function;
- Is a device malfunction or deterioration in the characteristics and/or performance of the device that results in death or serious deterioration in health;
- Is a device malfunction or deterioration in the characteristics and/or performance of the device that, if it were to occur again, could result in death or serious deterioration in health;
- Results in a congenital anomaly or birth defect.
- Is any medically significant injury, event or experience that requires medical/surgical intervention to prevent one of the outcomes listed above;
- Results in end- organ toxicity, including hematological, renal, cardiovascular, hepatic, gastrointestinal, and central nervous system events;

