9.1.7 Unanticipated Adverse Device Effects

An unanticipated adverse device effect as defined by the Federal Regulations [21 CFR 812.3(s)] is “any serious adverse effect on health or safety or any life-threatening problem or death caused by, or associated with, a device, if that effect, problem, or death was not previously identified in nature, severity, or degree of incidence in the investigational plan or application (including a supplementary plan or application), or any other unanticipated serious problem associated with a device that relates to the rights, safety, or welfare of subjects.” From a practical perspective, an unanticipated adverse device effect means a serious adverse event that is not listed in the device labeling, or the frequency or severity is greater than reported in the device labeling.

In the event of a serious (or unanticipated) adverse event, the Investigator will immediately notify the Venus Concept monitor by telephone. If such an adverse event is being reported after normal working hours, the Investigator will leave a voice message with accompanying report of the AE.

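### Section 10.14 triggers the site's ethics-committee report on severe device effects, so a serious or unanticipated effect not graded severe has, with one exception, no explicit site-to-committee report or time limit

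*Combined protocol and SAP*

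**What the plan says.** The protocol grades adverse events on two separate axes.

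- **Intensity (9.1.1).** Events are mild, moderate or severe: "Severe is used to describe the intensity of an event experienced by the subject".
- **Seriousness (9.1.3).** An event is serious if it meets one of a list of mainly outcome-based criteria, such as death, hospitalisation, permanent impairment, or an injury needing intervention to prevent impairment. The section opens with a warning: "The term serious is not synonymous with severity, which may be used to describe the intensity of an event experienced by the subject".

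Four sections then set reporting duties.

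- **9.1.6.** The investigator reports every anticipated event to the sponsor. If the sponsor or the investigator thinks it likely to affect subject safety or study conduct, the ethics committee is told within 10 working days of the sponsor's first notice.
- **9.1.7.** "In the event of a serious (or unanticipated) adverse event, the Investigator will immediately notify the Venus Concept monitor by telephone". No ethics committee is named.
- **9.2.1.** The heading reads "Adverse Events (AE) and Severe Adverse Events (SAE) Reporting", but the text covers serious events of any causality. They are telephoned to the clinical monitor immediately or within 24 hours, and then: "A written report must follow within five working days and is to include a full description of the event and sequence". No ethics committee is named.
- **10.14.** The site reports to both the sponsor's designee and the ethics committee. The outer limit is "in no event later than ten working days after the investigator first learns of the effect". The class of events that triggers this report is given as "any severe adverse device effect, whether anticipated or unanticipated, that occurs during the study as soon as possible".

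The abbreviation list in section 11 expands SAE as serious adverse event.

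**The concern.** 10.14 is the only section that gives the investigator a general duty, with a time limit, to report device effects to the ethics committee. It selects those events by intensity, although 9.1.3 warns that intensity and seriousness differ. Neither 9.1.7 nor 9.2.1, which do use the seriousness concept, sends anything to the committee.

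What is at stake is which events the committee overseeing subject protection hears about from the site, and when. A site that follows the text exactly would send a severe but non-serious skin reaction to its committee and could withhold a serious device effect graded moderate. Another site might read severe as a slip for serious and do the opposite. Safety is a primary objective (3.1), and up to 20 sites are named in the synopsis, so different readings between sites are a practical possibility.

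**Working it through.** No arithmetic underlies the main point. The check sets the reporting rules side by side and runs each type of device effect through them.

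**Step 1: the rules.**

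| Section | Event class | Recipient | Clock starts | Limit |
|---|---|---|---|---|
| 9.1.6 | Anticipated, judged likely to affect safety or conduct | Ethics committee | Sponsor's first notice | 10 working days |
| 9.1.7 | Serious or unanticipated | Sponsor's monitor | Not stated | Immediately, by telephone |
| 9.2.1 | Serious, any causality | Clinical monitor (sponsor's regulatory manager as backup) | Not stated | 24 hours by telephone, then written report in 5 working days |
| 10.14 | Severe device effect, anticipated or not | Sponsor's designee and ethics committee | Investigator's awareness | As soon as possible, at most 10 working days |

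**Step 2: device effects by class.**

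| Device effect | Sponsor told under 9.1.7 or 9.2.1? | Committee told under 10.14? |
|---|---|---|
| Serious and severe | Yes | Yes |
| Serious, mild or moderate | Yes | **No** |
| Severe, not serious | Only if unanticipated (9.1.7) | Yes |
| Neither | Only if unanticipated (9.1.7) | No |

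The second row is the gap. 9.1.6 fills it for one subset: effects on the anticipated list (blistering, burns, excessive edema or erythema, infection, PIH, scarring) that someone judges likely to affect safety or conduct. 9.1.6 does not say who notifies the committee. Unanticipated effects not graded severe stay uncovered.

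**Step 3: can the second row occur under the protocol's own definitions?** Yes. 9.1.1 allows a moderate event to need intervention and to leave sequelae. 9.1.3 makes an injury serious when intervention is needed to prevent permanent impairment. One injury can satisfy both. Also, 9.1.3 counts as serious a malfunction that could cause death or serious deterioration if it happened again. Such an event need not have reached severe intensity on this occasion, although the protocol does not say whether it counts as a device effect for 10.14.

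**Step 4: does anything else in 10.14 close the gap?** The 24-hour notice to the committee covers only emergency departures from the protocol. The five-working-day notice to the committee covers only device use without consent. Progress reports are made on request, and the final report is due within three months of the end of the study. None is a timed report of an individual event.

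**Step 5: the five- and ten-day limits.** Take a device effect that is both serious and severe. Assume the telephone call is made within 24 hours of the investigator learning of it (counted as at most one working day) and that the five days run from the call. The written report is then due by working day 1 + 5 = 6, inside the ceiling of 10. If the five days run from awareness, it is due by day 5. Either way, both limits can be met.

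**The case against.** The strongest reply is that this is one misplaced word with safeguards around it. Much of that stands.

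- **The terms overlap.** 9.1.1 describes severe events as needing intervention and leaving sequelae, so many serious injuries would be graded severe and reach the committee anyway. True, but moderate events may share both features, so the overlap is incomplete.
- **9.1.6 already provides a committee route.** It has no intensity threshold and covers the complications expected here. This stands as a limit on the gap. A reader might infer that every serious but non-severe effect lacks a committee deadline, and 9.1.6 shows that this is too broad. The route does depend on a judgement and leaves out unanticipated events.
- **Sites that are unsure must call the monitor (10.14).** That helps with doubtful cases but leaves the wrong criterion in place. A site certain that an event is not severe has no reason to call.
- **The study is committed to 21 CFR and ICH Good Clinical Practice (10.2).** Those texts may impose further duties. Their content is outside these documents, so neither a complete remedy nor non-compliance can be asserted.
- **The 9.2.1 heading is clerical.** Agreed: its text and section 11 both say serious. It shows that the terms were confused, and has no operative effect of its own.

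Two stronger readings are tempting and fail. One is that the five- and ten-working-day limits contradict each other. They cover different event classes and partly different recipients. The ten-day limit is a ceiling on reporting as soon as possible, and 10.14 does not call that report written. The other is that the safety record would be incomplete. Section 9.1 puts every adverse event in the source record and on the case report form, 9.2.1 sends every serious event to the sponsor's monitor, and 8.3 lists reported events with severity and relationship.

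**Conclusion.** The point holds in a limited form. As written, the 10.14 duty to report to the ethics committee is tied to an intensity grade that the protocol itself separates from seriousness. A serious or unanticipated device effect not graded severe therefore has no explicit site-to-committee report or time limit, unless it is an anticipated event that 9.1.6 brings in by judgement.

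Its size can be stated only as a class of events. The documents give no rates for serious or severe effects, so no count is possible. The five- and ten-day limits are merely unreconciled where one event falls under both rules. The conclusion rests on reading severe in 10.14 as 9.1.1 defines it. If serious was meant, the gap largely closes, but the text then still needs correcting and the two limits would cover the same serious device effects. Endpoints, sample size and analysis are unaffected. The correction should be made because it changes which events an ethics committee receives.

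**What to change.** 1. In 10.14, replace the severe trigger with the defined terms: serious adverse device effect (criteria of 9.1.3) and unanticipated adverse device effect (9.1.7). If the sponsor also wants severe but non-serious effects to go to the committee, list them as a separate class.
2. Correct the heading of 9.2.1 to say serious, in line with its text and section 11.
3. Reconcile 9.1.6, 9.1.7, 9.2.1 and 10.14 in one table giving event class, who reports, recipient, start of the clock and time limit. It should state the clock start that 9.2.1 omits, who notifies the committee under 9.1.6, and which limit governs an event that falls under two rules.

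The cost is protocol wording, with the approval that 10.10 requires for an amendment and a note to sites. Section 9.1 already has the investigator assess both severity and seriousness for each event, so no new data are needed.
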